## 6.2. Clinical Laboratory Tests

The following summary tables will be presented by type of laboratory test:

- Descriptive statistics will be calculated for each laboratory analyte (Hematology and Coagulation) for observed values at each scheduled time point.
- Parameters with predefined National Cancer Institute Common Terminology Criteria for Adverse Events (NCI-CTCAE, Version 4) toxicity grades at each scheduled time point of measurement
- The number and percentage of subjects with NCI-CTCAE grade >= 3 (markedly abnormal) for the parameters with predefined NCI-CTCAE toxicity grades at each scheduled time point of measurement
- Subjects with abnormal laboratory values at all measured time point.
- Subjects with any markedly abnormal laboratory results
- Normal reference ranges.

Since there is no conventional baseline visit, the values and abnormalities will be summarized by visit without change from baseline analysis. But the sensitivity analysis will be performed with baseline defined as Visit 1.

- Descriptive statistics will be calculated for each laboratory analyte (Hematology and Coagulation) at baseline and for observed values and changes from baseline at each scheduled time point.
- Shift tables (cross-tabulations) summarizing the shift in laboratory values from baseline to the worst post baseline measurement experienced by the subject during the study with respect to NCI-CTCAE toxicity grades
- Shift tables (cross-tabulations) summarizing the shift in laboratory values for non-graded parameters from baseline to each scheduled time point of measurement with respect to abnormality criteria (low, normal, high).
- For all participants, a listing to support the sensitivity analysis table will be provided which will include clinical laboratory test results and change from baseline at all measured time points.

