- f. All AEs and special situations following exposure to ibrutinib will be to be recorded in the CRF, regardless of seriousness or causality. AE collection should start from the time a signed and dated informed consent form is obtained and will apply to all adverse events that occur up until 30 days after a patient's last use within the study. It includes the incidence of deaths, AEs, and AEs reported/observed any time during the course of the study, either during any study visit or through any other mode of communication. AE follow-up required for 30 days after last dose to determine if any new or ongoing drug-related AEs or any SAEs regardless of relationship to ImbruvicaTM exists. Follow-up would be conducted by participating site via telephone contact.
- g. Investigations including haematological and coagulation profile
- h. A discontinuation visit is the visit at which the participating physician is discontinuing ImbruvicaTM or first routine clinic visit after the patient stopped taking ImbruvicaTM on his own. At the discontinuation visit information on date and reason(s) for ImbruvicaTM discontinuation will be collected, if available.
- i. For follow-up assessments, a telephonic follow-up call will be made by the participating physician 30 days (±7 days) after last dose of ImbruvicaTM or 30 days (±7 days) after completion of 12 months of ImbruvicaTM treatment (whichever is earlier), to inquire about any AEs observed.

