# 3.1. Overview of Study Design

Relapsed/refractory CLL and MCL patients who have received at least one therapy or CLL patients with deletion 17p selected by investigators and determined to be eligible for ibrutinib treatment as per protocol eligibility criteria will be enrolled in the study. Each subject will receive ibrutinib treatment for a period of 12 months or till disease progression, whichever is earlier. Enrolled subjects will be followed up to 12 months from the treatment initiation. During the study period, data will be collected at monthly intervals for the first 6 months, (monthly visit  $\pm$  7 days; Visit 1 to 6). Subsequent visit would be at 9 months  $\pm$  7 days [Visit 7]. The End-of-Treatment (EOT) visit will be conducted after the completion of 12-months ImbruvicaTM treatment (at Visit 8) or on the day at which the patient discontinued the ImbruvicaTM treatment or study. A telephonic follow-up will be conducted 30 days after the EOT Visit.

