## **Observation Visits (Visit 1 to Visit 8)**

The subjects will be followed up at every monthly interval during Visit 1 to Visit 6 for the first 6 months, followed by seventh visit at month 9 and eighth visit at month 12, and as outlined in the TIME AND EVENTS SCHEDULE The below mentioned procedure and measurements will be performed

- Current medical history (symptoms & signs if any, physical examination including vitals)
- Disease progression assessment
- Compliance Assessment
- Patient-completed PRO instruments (questionnaires and scales)
  - o FACIT Fatigue Instrument
  - o EORTC QLQ-30
- Type, dosage and duration of concomitant medication
- AEs for ImbruvicaTM (see Section
- Investigations (Hematology and coagulation profile); as per TIME AND EVENTS SCHEDULE.

**Note:** Visit 8 or discontinuation visit will be the EOT Visit.

A discontinuation visit is the visit at which the participating physician is discontinuing ImbruvicaTM or first routine clinic visit after the patient stopped taking ImbruvicaTM on his own.

At the discontinuation visit, information on date and reason(s) for ImbruvicaTM discontinuation will be collected, if available. The data for discontinuation visit will be collected on the EOT Visit page in CRF.

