#### 2. GENERAL ANALYSIS DEFINITIONS

The below mentioned general principles will be followed throughout the study:

- The change from baseline is defined as the post-baseline value minus the baseline value. Definition of baseline is provided in section 2.3.
- Descriptive statistics will include number of non-missing subject (n), mean, median, standard deviation (SD), minimum and maximum values for continuous variables, and for categorical variables the frequencies and percentages of subjects will be presented.
- For continuous data, mean and median will be rounded to 1 decimal place more than original data, SD will be rounded to 2 decimal places more than original data and minimum and maximum will be displayed with the same precision as the original data.
- For categorical data, percentages will be rounded to 1 decimal place.
- If a count is 0, the percentage (0%) should not be displayed. The 0 count will be displayed, but the corresponding percentage should be omitted.
- All study data will be included in study data listings. In general, all data will be listed by time point within subject.
- In general, missing data will not be imputed.
- SAS® version 9.4 will be used for all analyses.
- Visit Windows for PRO analysis:

To allow for variation in scheduling, the following set of visit windows will be used to assign evaluations to a most appropriate visit for analysis (Avisit).

Table 1A:

Visit	Avisit	Start Day	Target Day	End Day
SCR/Enrollment visit/Month 1	Screening	-	1	1
Visit 1/ Month 2 (end of month 1)	Month 1	2	30	37
Visit 2/Month 3 (end of month 2)	Month 2	38	60	67
Visit 3/Month 4 (end of month 3)	Month 3	68	90	97
Visit 4/ Month 5 (end of month 4)	Month 4	98	120	127
Visit 5/ Month 6 (end of month 5)	Month 5	128	150	157
Visit 6/ Month 7 (end of month 6)	Month 6	158	180	187
Visit 7/ Month 10 (end of month 9)	Month 9	188	270	277
Visit 8 (end of month 12/End of Treatment)	Month 12	278	360	367

8

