#### 6.4. ECOG Performance Status

Subjects will be listed with its performance status at all the schedule timepoints. Counts and percentages of ECOG will be presented at scheduled visits.

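### The Visit 8/EOT column for laboratory, vital-sign and ECOG data pools Month 12 completers with subjects who stopped early, because study-day windows are stated for PROs only

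*SAP*

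**What the plan says.** **One EOT visit.** Protocol section 5 (Observation Visits) states: "Visit 8 or discontinuation visit will be the EOT Visit". It adds: "The data for discontinuation visit will be collected on the EOT Visit page in CRF". The Time and Events Schedule has a single column for Visit 8 and EOT, and the discontinuation-visit row is marked in it. Laboratory tests are among the procedures for Visits 1 to 8 ("Investigations (Hematology and coagulation profile); as per TIME AND EVENTS SCHEDULE"), and vital signs with ECOG status are marked in the same column. Section 10.1 brings the last completed assessment of early stoppers into the analysis, without saying under which time point.

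**Summaries by scheduled visit.** SAP 6.2 on laboratory data: "Descriptive statistics will be calculated for each laboratory analyte (Hematology and Coagulation) for observed values at each scheduled time point". SAP 6.3 treats vital signs and their changes from baseline in the same way. SAP 6.4: "Counts and percentages of ECOG will be presented at scheduled visits". The only study-day windows are in Table 1A of SAP section 2, under the label "Visit Windows for PRO analysis". SAP 2.2 gives every safety assessment a study day, but no rule uses that day to set an analysis visit for these data.

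**Timing of EOT.** Protocol 3.1, the synopsis, the Treatment Period text and SAP 1.2 place EOT after 12 months of treatment "or on the day at which the patient discontinued the" drug or left the study. Footnote h of the schedule and section 5 instead use the visit at which the physician stops the drug or, for a subject who stops unprompted, the "first routine clinic visit after the patient stopped taking" it. They set no maximum interval.

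**The concern.** A subject who stops in Month 2 and one who completes Month 12 both supply a Visit 8/EOT blood count, coagulation profile, vital signs and ECOG score. Protocol section 4 names safety and progression as grounds for stopping treatment, so the early values come from a selected and probably sicker group. Pooled with completers, they can make the last column look worse than the Month 9 column when nobody who stayed on treatment has changed.

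This matters because the study is single-arm and descriptive, its primary objective is safety, and the synopsis names laboratory tests among the safety variables. No control arm shows the reader that the column is a mixture. SAP 6.1 ends the treatment-emergent period for AEs on the day of the last dose, but laboratory, vital-sign and ECOG values have no corresponding marker of treatment status.

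**Working it through.** The plan gives no figure on this point to reproduce. The 75 subjects are a committee recommendation, and no expected discontinuation rate is stated. The check follows values through the rules and then sizes the result under stated assumptions.

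**1. Follow one visit through both rules.** Take a subject whose discontinuation visit is on Day 45. The PRO scores fall in the Table 1A window of Days 38 to 67 and go to Month 2. The platelet count from the same visit is on the EOT page and has no window. Its scheduled time point is Visit 8/EOT, so it sits beside counts taken around Day 360.

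**2. Share of the column that is not Month 12.** Let N = 75, d = proportion stopping early (assumed) and a = proportion of those attending EOT (assumed). All completers are taken to have a Month 12 value. The number of early values is N·d·a, and their share is N·d·a / [N·d·a + N·(1 − d)]. The low end of d borrows 11.8%, the proportion stopping for an AE in the pooled monotherapy studies (Protocol 1.2). The other rates are assumptions.

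| d | Early stoppers | Completers | Share, a = 100% | Share, a = 70% |
|---|---|---|---|---|
| 11.8% | about 9 | about 66 | 11.8% | 8.6% |
| 20% | 15 | 60 | 20% | 14.9% |
| 30% | 22.5 | 52.5 | 30% | 23.1% |
| 40% | 30 | 45 | 40% | 31.8% |

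For example, with d = 40% and a = 70%: 75 × 0.40 × 0.70 = 21, and 21/(21 + 45) = 31.8%.

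**3. What selection alone could do.** Purely for illustration, assume a grade 3 or higher abnormality in 5% of completers and 25% of early stoppers, with all attending. The column shows 0.05(1 − d) + 0.25d:

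- d = 11.8%: 0.0441 + 0.0295 = 7.4%
- d = 40%: 0.030 + 0.100 = 13.0%

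The true Month 12 figure is 5% in both cases.

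**4. Possible delay after a self-stop.** If the next routine visit is the next scheduled one, the longest gap is the nominal spacing plus the ±7-day windows:

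- before Visit 1: 30 + 7 = 37 days
- between Visits 1 and 6: 30 + 14 = 44 days
- from Visit 6 to 7, or 7 to 8: 90 + 14 = 104 days

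These are upper limits. An earlier unscheduled contact would shorten them.

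**5. Would the existing windows be enough?** Under Table 1A, early EOT values on Days 45, 100 and 200 go to Months 2, 4 and 9. One on Day 300 still goes to Month 12, whose window is Days 278 to 367. Extending the windows clears most early values from Month 12. It does not clear those from Day 278 on, and it does not identify values taken after the last dose.

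**The case against.** **Pooling is inferred.** The SAP never says that early EOT values go into a Month 12 column. Its amendment history explains the windows in general terms, so wider use may have been meant. That is possible, but the label in section 2 limits them to PROs, and no other rule assigns the remaining data. If wider use was intended, the label needs correcting.

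**The size is unknown.** This stands. In Protocol 1.2, a 6-month PFS of 63% in an MCL study points to more early stopping. A 12-month PFS of 88% in relapsed CLL at 420 mg points to less. PFS events also include deaths, which supply no EOT sample. Only a range can be given.

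**Off-drug sampling.** A reader might infer that early EOT samples are generally drug-free, citing the half-life of 4.3 to 8.9 hours. The documents do not support this. When the physician stops the drug, that visit is the discontinuation visit, and the grounds for stopping in section 4 rest on the physician's assessment. The delay concerns only subjects who stop on their own, whose number is unknown. The half-life describes plasma concentration, whereas Protocol 1.1 describes irreversible BTK inhibition. Clearance from plasma therefore does not show that blood counts are free of drug effect.

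**Reach.** A reader might also infer that the main safety result is distorted. It is not: the TEAE endpoint is not tabulated by visit. The worst-grade shift table appears only in the laboratory sensitivity analysis and does not depend on visit assignment, although post-treatment values can enter it. Removing them would be debatable, because AEs are collected to 30 days after last use.

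**Recoverability.** The listings keep individual values and stop dates. This limits the harm but does not correct the summary column.

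**Conclusion.** The point holds as a weakness in the by-visit safety summaries. Followed as written, the plan produces a Visit 8/EOT column that mixes Month 12 values with values from early discontinuation visits, and the mixture can resemble late deterioration. Under an assumed early-stop rate of 11.8% to 40%, with all 75 subjects supplying a value, about 9 to 30 of those values would not be Month 12. Lower EOT attendance reduces this.

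The mixing of times applies to every early EOT visit. The further possibility of a sample weeks after the last dose applies only to self-stops, and it arises from two protocol accounts of EOT timing that must be reconciled. The primary endpoint is untouched, so this is a cheap and worthwhile improvement and not a threat to the study's main result.

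**What to change.** In SAP section 2:

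- Extend the Table 1A study-day windows to laboratory, vital-sign and ECOG data, and state which value is used when two fall in one window, since Table 1A does not say.
- Present Month 12 and end of treatment after early discontinuation as separate columns. The windows alone leave stops from Day 278 on in Month 12.
- Flag values taken more than a prespecified number of days after the last dose. Keep flagged values in the worst-value shift table and the listings, identified as post-treatment.

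In the protocol, reconcile the statements on EOT timing in the synopsis, section 3.1 and the Treatment Period text with those in footnote h and section 5, and align SAP 1.2. Record the days from last dose to EOT.

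The cost is fewer subjects in the Month 12 column, slightly more programming, and a short protocol clarification. Visit dates and drug stop dates are already planned (Protocol 17.4 and section 6), although the discontinuation date recorded at that visit is collected only where available, so some intervals may be missing.

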# 6.3. Vital Signs and Physical Examination

- Descriptive statistics of temperature, pulse/heart rate, respiratory rate, mean arterial pressure
  and blood pressure (systolic and diastolic values) and changes from baseline will be
  summarized at each scheduled time point
- The percentage of subjects with values beyond clinically important limits will be summarized.
- Listing of vital sign measurements and the change from baseline will be presented for all participants.
- A listing of abnormal vital signs will be presented, including unscheduled visits.

**Table 4: Normal Ranges for Vital Signs** 

Parameter	Range	Unit
Body temperature	36.1 – 37.2	С
Pulse rate	60 – 100	beats/min
Systolic Blood Pressure	90 – 120	mmHg
Diastolic Blood Pressure	60 – 80	mmHg
Mean Arterial Pressure	70 - 100	mmHg
Respiratory Rate	12 – 20	breaths/min

Physical examination findings will be listed.

#### 6.4. ECOG Performance Status

Subjects will be listed with its performance status at all the schedule timepoints. Counts and percentages of ECOG will be presented at scheduled visits.

